7.7. Monitoring Plane limb

A separate document for the study monitoring plan will be developed and followed to ensure subject safety and GCP compliance.

8. STATISTICAL DESIGN AND ANALYSIS

This is a validation study for Masimo INVSENSOR00073, which follows the *ISO 81060-2-2018 Non-invasive sphygmomanometers- Part 2: Clinical investigation of intermittent automated measurement type requirements*.

8.1. Sample size

According to ISO 81060-2:2018, a minimum of 150 valid data points from a minimum of 15 subjects are required; no more than 10 measurements per subject is permitted. Additionally, the following requirements pertaining to sex distribution, limb size distribution, and pre-specified blood pressure distribution shall be met:

- Minimum of 30% of participants are to be male and 30% female (i.e., minimum of 5 males and 5 females).
- At least $1/2n$ of participants tested with each cuff size, where n is the number of cuff sizes. Accordingly, at least three participants tested with each of the cuff sizes of small, medium, and large.
- Data shall meet blood pressure distribution requirements as follows:
 - At least 10% of shall have a reference systolic blood pressure (SBP) ≤ 100 mm Hg.
 - At least 10% of shall have a reference SBP ≥ 160 mm Hg.
 - At least 10% of shall have a reference diastolic blood pressure (DBP) ≤ 70 mm Hg.

² IV may be placed during screening/baseline to obtain qualifying venous sample at discretion of medical staff. If the IV is placed during screening/baseline, medical staff will offer to use local anesthetics.

³ Adverse events may be reported by the subject after their visit. See section 14 for additional details.

* At the discretion of the study staff

- At least 10% of shall have a reference DBP \geq 85 mm Hg.

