2. OVERALL SYNOPSIS OF THE CLINICAL INVESTIGATION

Clinical investigation title:	Validation Study of Mean Arterial Pressure (MAP) Parameter of Masimo INVSENSOR00073
Study objective(s):	The objective of this study is to validate the Mean Arterial Pressure (MAP) parameter of Masimo INVSENSOR00073 against the gold standard blood pressure measurements from the arterial line.
Study device under test:	Masimo INVSENSOR00073
Number of participants:	Approximately 20.
Inclusion criteria:	
Influenced by study design:
 
• Subject is 18 to 40 years of age.• Subject weighs a minimum of 110 lbs.• Baseline heart rate \geq 45 bpm and \leq 90 bpm.• Baseline blood pressure: Systolic blood pressure \leq 135 mmHg and \geq 100 mmHg. Diastolic blood pressure \leq 95 mmHg and \geq 55 mmHg. Valid systolic blood pressure (SBP) auscultatory measurements for lateral difference is \leq 15 mmHg. Valid diastolic blood pressure (DBP) auscultatory measurements for lateral difference is \leq 10 mmHg.• Hemoglobin value \geq 11 g/dL.• CO value \leq 3.0% FCOHb.• Subject is comfortable to read and communicate in English*. 
* This is to ensure the subject can provide informed consent (as study materials are currently available in English only) and can comply with study procedures.

Exclusion criteria:	
Influenced by device warning labels:
 
• Subject is pregnant or breastfeeding.• Subject is experiencing dysrhythmia or arrhythmia. 
Influenced by study design/environment:
 
• Subject is concurrently participating in another research study.• Subjects not suitable for the investigation at the discretion of the clinical team including but not limited to the items below.
○ Subjects who do not pass the health assessment for safe participation in the study procedures.○ Inability to insert or difficulty with inserting an intravenous line in the subject's hand or arm and/or an arterial line in the radial artery of the subject's wrist.
Groups:	A targeted enrollment approach will be used to ensure ISO 81060-2-2018 ⁽¹⁾ requirements (specified under section 7.5.3) pertaining to sex, cuff size, and blood pressures distributions are met.

Study Title: Validation Study of Mean Arterial Pressure (MAP) Parameter of Masimo
INVSENSOR00073

Revision: 

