Duration of the clinical investigation:	The expected duration of study enrollment is 1 to 3 months. Subject participation in the study will be approximately 180 minutes.
Study endpoint(s):	Accuracy and precision of mean arterial pressure (MAP) measured by Masimo INVSENSOR00073, in adult or adolescent patients, in comparison to radial arterial line.

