7.5. Subjects

7.5.1. Inclusion Criteria

Influenced by study design:

- Subject is 18 to 40 years of age.
- Subject weighs a minimum of 110 lbs.
- Baseline heart rate ≥ 45 bpm and ≤ 90 bpm.
- Baseline blood pressure:

Systolic blood pressure ≤ 135 mmHg and ≥ 100 mmHg.

Diastolic blood pressure ≤ 95 mmHg and ≥ 55 mmHg.

If systolic blood pressure is lower than 100 mmHg and/or diastolic blood pressure is lower than 60 mmHg, subject passes an orthostatic blood pressure test.

Valid systolic blood pressure (SBP) auscultatory measurements for lateral difference is ≤ 15 mmHg.

Valid diastolic blood pressure (DBP) auscultatory measurements for lateral difference is ≤ 10 mmHg.

- Hemoglobin value ≥ 11 g/dL.
- CO value $\leq 3.0\%$ FCOHb.
- Subject is comfortable to read and communicate in English*.

* This is to ensure the subject can provide informed consent (as study materials are currently available in English only) and can comply with study procedures.

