7.6.3.3. Blood Pressure Variations Procedure

During the blood pressure variations procedure, participants will be administered continuous infusions containing vasoactive medications. There will be two study types:

[figure not shown]
[figure not shown]
Induced controlled hypertension (increased blood pressure)

Induced controlled hypotension (decreased blood pressure)

Both study types will involve the use of a primary drug to elicit the desired blood pressure change.

Vasoactive Medication

[figure not shown]
[figure not shown]
 will be used as the primary drug to induce hypertension (increased blood pressure) and  will be used to induce hypotension (decreased blood pressure).

Study Title: Validation Study of Mean Arterial Pressure (MAP) Parameter of Masimo
INVSENSOR00073

Revision: 

Safety drugs will be used to counteract the effects of the primary drugs when deemed necessary by the presiding clinician. Table 1 outlines the possible primary and safety drug choices based on the pressure variation study type.

Table 1. Drugs allowed for pharmacological variations of blood pressure variation studies.

Type of Pressure Variation Study	Primary Drug	Safety Drug
		
		

Blood Pressure Safety Limits

Medication-induced blood pressure variation studies have strict pressure variation limits to ensure the subject's blood pressure stays within a safe range. Tables 2 and 3 below outline the maximum allowable pressure variations for each study type. If the blood pressure limits are reached or exceeded, drug infusion will be stopped immediately, and the subject will be monitored as blood pressure returns to the baseline values. The study may be continued if the subject is comfortable, and clinicians deem it is safe to proceed.

Target blood pressure changes must be determined prior to starting the study for each subject. The selected variation must be the lesser of the percent and absolute changes indicated in Table 2, provided the selected variation does not violate the limits established in Table 3. Vasoactive medications are titrated based upon the arterial line-derived mean arterial pressure (MAP) reading. Blood pressures must remain within the limits defined in Table 3 for the duration of the procedure.

Table 2. Maximum allowed pressure variations for each study type. Target pressure variations are calculated based on mean arterial pressure (MAP)

Study Type	Percent Change From Baseline MAP	Absolute Change From Baseline MAP
Controlled Hypertension		

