8.2.2. Acceptance Criteria

- Mean error of ≤ 5 mmHg with a standard deviation of ≤ 8 mmHg.

Per *ISO 81060-2-2018 Non-invasive sphygmomanometers- Part 2: Clinical investigation of intermittent automated measurement type*, the mean value of the errors for systolic and diastolic blood pressures shall be within or equal to 5.0 mmHg with an experimental standard deviation no greater than 8.0 mmHg. The validation of Mean Arterial Pressure (MAP) for Masimo INVSENSOR00073 shall follow these requirements.

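### Section 8.1 sets its pressure-range requirement on SBP and DBP only, so the plan does not guarantee that MAP, the endpoint, is tested at low and high values

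*Combined protocol and SAP*

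**What the plan says.** The stated objective (section 2) is to "validate the Mean Arterial Pressure (MAP) parameter of Masimo INVSENSOR00073 against the gold standard blood pressure measurements from the arterial line", and the endpoint is "Accuracy and precision of mean arterial pressure (MAP) measured by Masimo INVSENSOR00073". Section 8.2.1 computes the mean and standard deviation of the MAP errors. Section 8.2.2 takes the limits that the cited standard sets for SBP and DBP errors (mean within 5 mmHg, standard deviation at most 8 mmHg) and adds: "The validation of Mean Arterial Pressure (MAP) for Masimo INVSENSOR00073 shall follow these requirements".

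Section 8.1 introduces the required spread with "Data shall meet blood pressure distribution requirements as follows" and lists four quotas of at least 10% each: reference SBP at or below 100, SBP at or above 160, DBP at or below 70, and DBP at or above 85 mmHg. It sets no quota on reference MAP and no joint condition on SBP and DBP. Section 7.3 treats the study as complete once the subjects and data points described in 8.1 have been obtained.

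MAP does appear in the procedure. Section 7.6.3.3 states: "Vasoactive medications are titrated based upon the arterial line-derived mean arterial pressure (MAP) reading". Its Table 2 is headed "Maximum allowed pressure variations for each study type", and its Table 3 lists minimum and maximum levels, including a MAP row. The numbers in both tables are blacked out.

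**The concern.** Section 4 justifies the drug-induced pressure changes by the need to test the device across a pre-specified pressure distribution. For the parameter being validated, no such distribution is specified. Section 8.2.2 explicitly carries the accuracy limits over from SBP and DBP to MAP, but nothing carries the range requirement over.

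A reading with high SBP and middling DBP has a middling MAP, and so does one with high DBP and ordinary SBP. Both DBP cut-points, 70 and 85, lie inside the entry range of 55 to 95, so resting readings could fill those two quotas.

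The analysis is a pooled mean and standard deviation, with no planned look at error against reference MAP. If the MAP data clustered in the middle, the result would not show it. The study could complete and pass while saying little about accuracy at low or high MAP, and the validation statement would carry no range.

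**Working it through.** **The plan's own figures.** 15 subjects × 10 readings = 150. At 15 subjects, 30% of each sex is 4.5, rounded up to 5. With three cuff sizes, 15/(2 × 3) = 2.5, rounded up to 3. These match section 8.1. Each pressure quota is 10% of 150 = 15 readings. (The quota bullets omit the noun after the percentage; I read it as valid readings.)

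**Inputs.** Quota cut-points come from section 8.1. Entry limits come from section 7.5.1: "Systolic blood pressure ≤ 135 mmHg and ≥ 100 mmHg", with DBP 55 to 95 mmHg. (A further clause there, on subjects below those SBP limits, does not fit the SBP floor of 100 and needs reconciling; I use 100.) The plan reads reference MAP from the arterial-line monitor and gives no formula linking it to SBP and DBP, so I assume MAP = DBP + k(SBP - DBP), with k = 1/3 as base and 0.40 and 0.50 as alternatives.

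**How far the SBP quotas constrain MAP.** With pulse pressure PP = SBP - DBP, the formula becomes MAP = SBP - (1 - k)PP. A reading with SBP of at least 160 and one with SBP of at most 100 therefore differ in MAP by at least

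60 - (1 - k)(PP of the high reading - PP of the low reading).

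At k = 1/3 and equal pulse pressures this is 60 mmHg. The span shrinks only as the pulse pressures diverge.

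**A data set that meets every quota (k = 1/3).**

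| Share | SBP/DBP | PP | MAP | Quota met |
|---|---|---|---|---|
| 10% | 160/75 | 85 | 103.3 | SBP ≥ 160 |
| 10% | 130/85 | 45 | 100.0 | DBP ≥ 85 |
| 10% | 100/72 | 28 | 81.3 | SBP ≤ 100 |
| 10% | 115/70 | 45 | 85.0 | DBP ≤ 70 |
| 60% | 120/75 | 45 | 90.0 | none |

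The span is 103.3 - 81.3 = 22.0 mmHg, which agrees with 60 - (2/3)(85 - 28) = 22.0. A second set, 100/70, 160/70 and 130/85, gives MAP 80, 100 and 100, a span of 20.

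**Yardstick from entry limits (k = 1/3).** 100/55 gives MAP 70.0 and 135/95 gives 108.3, a span of 38.3. The SBP bound falls below this when (2/3) × (PP difference) exceeds 60 - 38.3 = 21.7, that is, when pulse pressures differ by more than 32.5 mmHg.

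**Sensitivity to k.**

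| k | Entry span | Table example | 100/70, 160/70, 130/85 |
|---|---|---|---|
| 1/3 | 38.3 | 22.0 (81.3 to 103.3) | 20.0 |
| 0.40 | 38.0 | 25.8 (83.2 to 109.0) | 24.0 |
| 0.50 | 37.5 | 31.5 (86.0 to 117.5) | 30.0 |

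**Sensitivity to pulse pressure (k = 1/3).** A grid search for the smallest span meeting all four quotas gives 20.0 mmHg if pulse pressures run from 30 to 90, 26.7 for 30 to 80, 33.3 for 30 to 70, and 40.0 for 30 to 60. In the last case the span exceeds the entry span.

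**What the pooled SD would show.** In the table example (15, 15, 15, 15 and 90 readings) mean reference MAP is 91.0 and its SD is 6.1 mmHg. Suppose, as an assumption, that device error changes by 0.2 mmHg per mmHg of MAP. This contributes a component of SD 0.2 × 6.1 = 1.2 mmHg. If all other error had SD 7.0 (also assumed) and were independent of MAP, the total would be √(7.0² + 1.2²) = 7.1, within the limit of 8. The trend would go unnoticed unless error was examined against MAP.

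**The case against.** Four points can be made for the plan.

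- **The quotas are not empty for MAP.** A reader might infer that nothing in 8.1 constrains MAP. The bound above shows otherwise: with similar pulse pressures the SBP quotas alone force a wide MAP span. The narrow example needs pulse pressures of 85 and 28 in the same data set. This stands, and it limits the point to a missing guarantee.
- **The procedure drives MAP.** Entry SBP is at most 135, so readings at 160 or above would come mainly from induced hypertension, which is titrated on arterial-line MAP towards a target set beforehand for each subject. This makes clustering of MAP less likely. It does not secure coverage: Table 2 gives maximum changes, Table 3 gives safety bounds, and section 4 lets a subject take part in hypertension and/or hypotension, so no mix is fixed. With the numbers blacked out, the intended size of the MAP excursion cannot be judged.
- **The entry-range comparison is uneven.** A reader might infer that the trial would cover less MAP than its volunteers show at rest. The 38 mmHg figure is the largest range that entry could allow, set against the smallest that the quotas could produce. Entry guarantees no data at either corner, so the figure serves only as a yardstick.
- **The quotas are presented as those of the cited standard.** Whether that standard expects a MAP quota cannot be checked from the documents, so no departure from it is alleged. The plan did, however, extend the accuracy limits to MAP itself, and the range requirement could be extended in the same way.

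**Conclusion.** The gap is real but limited. The plan contains no requirement that the analysed data include low and high reference MAP, and its quotas secure that only indirectly. Under the assumed formula with k = 1/3, they can be met with reference MAP of about 80 to 103 mmHg. For the span to fall below 38 mmHg, pulse pressures in the data must differ by more than about 32.5 mmHg, which the plan neither expects nor excludes. At larger k the spans widen, but both example sets stay narrower than the entry span up to k = 0.50.

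The documents do not show that the trial will end with mid-range MAP only; MAP-based titration points the other way. Nor do they support particular MAP cut-points. Pairing the plan's limits as 100/70 and 160/85 gives 80 and 110 at k = 1/3 but 82 and 115 at k = 0.40. The plan never makes those pairings, and the blacked-out tables prevent a check that such values can be reached. What follows is that the validation claim needs a stated MAP range and an analysis showing how error behaves across it.

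**What to change.** 1. In 8.2.1, pre-specify that the distribution of reference MAP will be reported, together with device error against reference MAP, for example as mean error and SD in low, middle and high MAP bands set in advance.
2. In 8.2.2, state that the MAP validation claim extends only to the reference-MAP range actually covered by the data.
3. Where the existing Table 2 and Table 3 limits already permit it, add to 8.1 that at least 10% of valid readings lie below a low reference-MAP cut-point and at least 10% above a high one. The sponsor, who holds the blacked-out values, should fix both cut-points before data collection. Titration and safety limits stay as they are.

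The cost is a few sentences in 8.1 and 8.2, a little more analysis, and possibly a narrower stated MAP range. Items 1 and 2 need no new procedure or equipment and can be adopted even if item 3 proves infeasible.

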8.2. Data Analysis

The resonant frequency and damping coefficient of the reference invasive blood pressure monitoring equipment shall be characterized.

8.2.1. Accuracy Calculations

Mean error and standard deviation for the MAP measurements from the Masimo INVSENSOR00073 device under investigation in comparison with measurements from the reference invasive radial arterial line (A-line) will be calculated.

Since the opposite limb is used for reference site of intra-arterial blood pressure recording, the results shall be corrected for the lateral difference. The lateral difference will be calculated as the average difference between the reference readings or determinations made on each limb according to the formula (1) below:

$$(1) \text{ Lateral Difference: } LD = \frac{1}{3} \times (\sum_{i=1}^3 p_i - \sum_{j=1}^3 p_j),$$

Where i is the index for the determination on the limb used for the sphygmomanometer-under-test determination, and j is the index for the reading on the limb used for the reference reading.

Lateral difference will be calculated for each subject prior to taking invasive measurements, using two identical automated sphygmomanometers. If the lateral difference of the reference systolic blood pressure is > 15 mmHg or the lateral difference of the reference diastolic blood pressure is > 10 mm Hg, subject will not participate in the study.

For those who are eligible to participate in the invasive measurement, sphygmomanometer-under-test error, x , is calculated by taking the difference between the sphygmomanometer-under-test blood pressure and the reference blood pressure and by adding the lateral difference (LD) if the sphygmomanometer-under-test blood pressure was taken in the left arm, according to formula (2), or subtracting LD if the sphygmomanometer-under-test blood pressure was taken in the right arm, according to formula (3).

$$(2) \text{ Sphygmomanometer-under-test error (worn on left arm), } x = p_{SUT_L} - p_{REF_R} + LD,$$
$$(3) \text{ Sphygmomanometer-under-test error (worn on right arm), } x = p_{SUT_R} - p_{REF_L} - LD,$$

Where p_{SUT_L} and p_{SUT_R} are sphygmomanometer-under-test blood pressures in the left (L) and right (R) arms, respectively; and similarly, p_{REF_L} and p_{REF_R} are reference blood pressures in the left (L) and right (R) arms, respectively.

The reference MAP will be read from the values displayed on the reference invasive blood pressure monitoring equipment. Since the recording is not interrupted due to cuff inflation, the reference blood pressure ranges shall be determined from the recording of the invasive blood pressure for a duration of at least 30 seconds that includes the period of determination of INVSENSOR00073. Specifically, 30 seconds of reference recordings prior to the determination of INVSENSOR00073 will be used. Reference recordings and determination of Masimo INVSENSOR00073 will be synchronized based on the time stamp of the data acquisition device.

For the sphygmomanometer-under-test, the mean value of the errors \bar{x}_n and experimental standard deviation s_n of the n individual paired determinations of the Masimo INVSENSOR00073 for all subjects shall be calculated according to the formulas (4) and (5) below:

$$(4) \text{ Mean Error: } \bar{x}_n = \frac{1}{n} \times \sum_{i=1}^n x_i$$

$$(5) \text{ Standard Deviation: } s_n = \sqrt{\frac{1}{n-1} \times \sum_{i=1}^n (x_i - \bar{x}_n)^2},$$

where x_i is the error of the i^{th} individual determination, n is the total number of determinations, and i is the index for the individual determination.

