3. DESCRIPTION OF THE INVESTIGATIONAL DEVICE

 is a continuous, scalable, patient-worn, vital signs monitor , which provides the versatility of a bedside monitor in a wearable device.

 monitors a wide range of physiological parameters. Designed to scale up or down with patient acuity,  combines the reliability and accuracy of a bedside monitor with the comfort and freedom of a wearable device, allowing for ambulation and movement during continuous monitoring. Suitable for use across the continuum of care,  offers advanced flexibility and is easily scalable to accommodate surges in patient volume and each patient's level of acuity.

The focus of this study is on the validation of the mean arterial pressure (MAP) parameter of Masimo INVSENSOR00073. Masimo INVSENSOR00073 provides systolic, diastolic, and mean arterial blood pressure readings through an oscillometric method. An oscillometric method of blood pressure measurement is a noninvasive method that monitors the amplitude of cuff pressure changes during cuff deflation to determine arterial blood pressure. Masimo INVSENSOR00073 consists of a reusable module and a disposable cuff, which plug into the  device, or a laptop for data collection purposes.

For blood pressure measurements, the cuff is wrapped around the non-dominant arm, making sure that the cuff's Artery Marker is aligned over the brachial artery. To locate the brachial artery, one should place the pads of his/her index and middle fingers halfway between the shoulder and elbow, in the middle of the inner arm, between the biceps and triceps muscles. The cuff should fit comfortably around the patient's arm for maximum oscillometric signal quality. The lower edge of the cuff should be located 2 cm above the antecubital fossa (interior bend of the elbow).

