7.6.2.2. Health Assessment and Eligibility Determination

After informed consent, subjects will be screened to determine eligibility for study enrollment and safe participation in the study. Subjects must meet all inclusion criteria and none of the exclusion criteria to participate in the study. All subjects screened will be documented on the *Screening and Enrollment Log*. Subjects who do not meet the eligibility criteria will be considered screen failures and the reason for the status of screen failure will be documented on the *Screening and Enrollment Log*.

Information on subject demographics (including but not limited to sex, race and ethnicity, skin pigmentation, age, height, and weight), arms circumference, and a medical history may be collected.

- Pregnancy Screening:

Female subjects will be required to take a pregnancy test. Subjects will be notified of their pregnancy result and the result will be noted. Subjects will be excluded from the study if the result is positive.

- Vital Signs Screening:

Vital signs such as blood pressure, heart rate, and pulse oximetry measurements such as SpO₂, SpCO, and SpHb may be checked and recorded for subject safety monitoring.

Transient increases in blood pressure and heart rate can be expected during line placement, needle sticks, blood draw, etc. and may also be attributed to anxiety/nervousness relating to a new environment. For most participants, only the initial recorded blood pressure and/or heart rate determines a subject's qualification for the study. In the case where heart rate and blood pressure changes suggest participant discomfort or a potential safety concern, the participant will be removed from the study after qualifying, according to the discretion of medical and study staff.

Assessment of lateral difference in blood pressure measurements between the left and right arms will be done with simultaneous blood pressure reading in both arms. Simultaneous blood pressure reading in both arms will be performed using FDA-cleared auscultatory measure three times, following best practices (e.g., positioning the middle of the cuff on the patient's upper arm at the level of the right atrium [the midpoint of the sternum]). Study will only proceed if the lateral difference is ≤ 15 mmHg for the systolic blood pressure (SBP), and ≤ 10 mmHg for the diastolic blood pressure (DBP). Otherwise, the subject will be withdrawn from participating in the study.

- Venous and Arterial Access Screening:

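### The lateral difference comes from two automated units with no stated exchange or cross-check, so a fixed offset between them can shift the mean error by up to its full size

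*Combined protocol and SAP*

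**What the plan says.** The test cuff goes on the limb opposite the arterial line (section 7.6.3.2), and section 8.2.1 draws the consequence: "Since the opposite limb is used for reference site of intra-arterial blood pressure recording, the results shall be corrected for the lateral difference". LD therefore enters every paired error.

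Formula (1) is the mean of three test-limb readings minus the mean of three reference-limb readings: "Where i is the index for the determination on the limb used for the sphygmomanometer-under-test determination", with j for the other limb. Formula (2) forms the error "by adding the lateral difference (LD) if the sphygmomanometer-under-test blood pressure was taken in the left arm". Formula (3) forms it by "subtracting LD if the sphygmomanometer-under-test blood pressure was taken in the right arm".

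On the instrument, section 8.2.1 says: "Lateral difference will be calculated for each subject prior to taking invasive measurements, using two identical automated sphygmomanometers". Section 7.6.2.2 describes the assessment differently: "Simultaneous blood pressure reading in both arms will be performed using FDA-cleared auscultatory measure three times". The inclusion criterion in 7.5.1 agrees with 7.6.2.2: "Valid systolic blood pressure (SBP) auscultatory measurements for lateral difference is ≤ 15 mmHg". The synopsis (section 2) repeats that criterion.

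On which arm carries the test cuff, the device description in section 3 says "the cuff is wrapped around the non-dominant arm". No share of left arms is given.

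The readable text has no rule for which unit goes on which arm, no exchange between arms, no comparison of one unit with the other, and no tolerance for a difference between them.

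**The concern.** With one unit on each arm throughout, the observed LD is the true arm difference plus the difference in calibration between the units, and these data cannot separate the two. Averaging three readings reduces random reading error but leaves a constant offset untouched. Calling the units identical sets no limit on how far they may disagree. If two observers each listened on one arm, a constant difference between observers would act in the same way.

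The mean error is judged against a fixed limit of 5 mmHg and the SD against 8 mmHg (section 8.2.2). An offset introduced by the correction is not error of the device under test, yet it counts for or against the device. For a device whose true bias is near the limit, it could change the result in either direction.

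**Working it through.** **Inputs from the plan.** At least 15 subjects with at most 10 readings each (8.1); limits of 5 and 8 mmHg (8.2.2); formulas (1) to (4) (8.2.1). The minimum number of data points reproduces: 15 × 10 = 150.

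**Assumed inputs.** The offset d between units on the pressure being corrected, range 1 to 3 mmHg, and the share pL of subjects with the test cuff on the left. The documents give neither.

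**Step 1: units kept on one side, formulas as printed.** Let the left-arm unit read d higher than the right-arm unit.

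- Left cuff: observed LD = true LD + d. Formula (2) adds LD, so the error shifts by +d.
- Right cuff: observed LD = true LD − d. Formula (3) subtracts LD, so the error shifts by −(−d) = +d.

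Both arms shift by +d, so the mean error shifts by d whatever pL is. For d = 1, 2, 3 mmHg this is 1/5, 2/5 and 3/5 of the limit: 20%, 40%, 60%.

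**Step 2: other ways of assigning units or signs.**

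| Assignment | Signs | Shift in mean error |
|---|---|---|
| Fixed to side | as printed | d |
| Fixed to test limb | as printed | d(2pL − 1): d at pL = 1, 0.8d at 0.9, 0 at 0.5 |
| Fixed to side | LD subtracted on both arms | −d(2pL − 1) |
| Fixed to test limb | LD subtracted on both arms | −d |
| Random by subject | either | expected 0 |

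Under random assignment the shift has SD d/√15 = 0.26, 0.52, 0.77 mmHg for d = 1, 2, 3 (0.22, 0.45, 0.67 with 20 subjects). The error variance rises by about d². An SD of 7.5 becomes √(56.25 + d²) = 7.57, 7.76, 8.08, so at d = 3 it passes the 8 mmHg limit.

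**Step 3: effect on pass or fail.** Assume a between-subject SD of 4 and a within-subject SD of 5, with 15 × 10 readings. The standard error of the mean is √(16/15 + 25/150) = 1.11 mmHg. Simulated probability of meeting both limits, 40,000 studies per scenario:

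| True bias | No offset | d = 1 | d = 2 | d = 3 |
|---|---|---|---|---|
| 6 mmHg, fixed offset toward zero | 0.18 | 0.50 | 0.81 | 0.96 |
| 6 mmHg, random assignment | 0.18 | 0.19 | 0.20 | 0.22 |
| 4 mmHg, fixed offset away from zero | 0.81 | 0.50 | 0.19 | 0.04 |

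The normal approximation agrees for the first row. The mean meets the limit with probability Φ(−1/1.11) = 0.18 with no offset, and 0.50, 0.82, 0.96 with offsets of 1, 2, 3. At zero true bias the effect is small: 0.997 with no offset and 0.96 at d = 3.

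**Step 4: effect of exchanging units.** Two pairs each way leave (d + d − d − d)/4 = 0 in LD, so nothing remains under either sign rule. A 2/1 split of three pairs leaves (d + d − d)/3 = d/3, or 0.33, 0.67, 1.00 mmHg.

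**The case against.** A reader might infer that any offset must pass straight into the mean error and that more subjects cannot reduce it. The documents do not support this. Both statements need each unit to be tied to a side, or to the test limb, and no such rule is stated. Under haphazard assignment the expected shift is 0, its SD falls with the number of subjects, and the cost moves to the SD of the errors. This limits the claim to what can happen. It does not remove the concern, because nothing in the plan prevents the fixed case.

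A reader might also argue that the bias arises because non-dominant arms are mostly left arms. With the printed formulas and units kept on one side, that is not the mechanism: the shift is d at any share of left cuffs.

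Four further objections have weight.

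- The absence of an exchange is silence, not a stated rule. Part of the text is also missing from the available copy: the research equipment list (7.4), the schedule (7.6.4) and the workflow appendix. The claim therefore covers readable text only.
- The instrument is unsettled. Only 8.2.1 says automated, and simultaneous readings are mentioned only in the auscultatory description in 7.6.2.2. Neither reading provides a safeguard, although no section mentions two observers.
- The size of d is assumed, and two identical units may differ little. The plan sets no tolerance that would show this.
- The offset also enters the 15 and 10 mmHg eligibility check, but the documents give no figures from which to size that effect.

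**Conclusion.** The point holds in conditional form. The plan states neither an exchange of units (or observers) between arms nor a check of one against the other, so a fixed offset of d can move the mean error by as much as d. With the printed formulas and units kept on one side, the move is the full d: 1 to 3 mmHg for the assumed range, or 20% to 60% of the limit. With haphazard assignment the mean is about unaffected in expectation and the error variance grows by about d².

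The result rests on an assumed d and an unstated assignment rule. The pass probabilities also rest on assumed SDs, and they matter mainly for a device whose true bias lies near 5 mmHg. The change is worth making because it removes an avoidable source of bias at almost no cost.

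The sign conflict between formulas (1) and (2) is a separate issue: test limb minus reference limb is added for a left cuff. The conclusion here does not depend on how it is settled, since an exchange of units cancels the offset under either convention.

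**What to change.** 1. Reconcile sections 2, 7.5.1 and 7.6.2.2 (auscultatory) with 8.2.1 (automated), so that one method for measuring LD is stated throughout.
2. In 7.6.2.2 and 8.2.1, specify two pairs of readings, an exchange of the two units (or observers) between arms, then two more pairs. Change formula (1) to a factor of 1/4 with sums to 4. Record which unit was on which arm for each pair.
3. If three pairs must be kept, exchange after one or two pairs and alternate the 2/1 order by subject, balanced within cuff side. This leaves d/3 in each subject and about 0 in the mean error. The added variance is about d²/9, so at d = 3 an SD of 7.5 becomes √(56.25 + 1) = 7.57.

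Alternating units by subject without an exchange is second best: it protects the mean but adds about d² to the variance.

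The cost is at most one extra pair of cuff readings per subject before the invasive measurements, plus one formula and a few sentences. The four-pair version departs from the three-reading formula. The sponsor should confirm that the standard the plan follows allows this, which cannot be checked from these documents.
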